The severe acute respiratory syndrome coronavirus 2 (SARS-CoV-2), which causes COronaVirus Disease 2019 (COVID-19), has resulted in a worldwide pandemic and currently represents a major public health (1). The SARS-CoV-2 virus, an acute respiratory infectious agent, is primarily transmitted between people through respiratory droplets and contact routes (2,3). A recognized key to transmission of COVID-19, and droplet infections generally, is the dispersion of bio-aerosols from the patient. Bio-aerosols are defined as aerosols or particulate and matter of animal, plant or microbial origin with a range from 0.1 to >100 µm in diameter (4), that can contain viruses, bacteria, fungi, and are generated by infected persons when they cough, sneeze, talk, sing, or breathe. They can land in the mouth, nose, or eyes of those in proximity, and they have the potential to be inhaled into the lungs.

National and international guidelines recommend droplet/airborne and contact precautions for those caring for COVID-19 patients in ambulatory and acute care settings (5-9). An increased risk of transmission has been associated with aerosol generating procedures, including nebulised treatment. Despite the lack of evidence, there is currently a heightened concern regarding the potential risk of transmission of SARS-CoV-2 in the form of aerosolised respiratory droplets from patients with COVID-19 undergoing nebulised treatment (9,10). Studies regarding risk of spreading the virus in the environment during nebulisation are conflicting. For example, one study reports not to find the virus in hospital air samples near COVID-19 patients (11); in contrast, another study conducted using a manikin in a laboratory detected the virus at a distance of two meters (12). Despite the absence of any robust scientific evidence, some guidelines have advised against the

use of nebuliser treatment unless absolutely necessary, others have recommended the continued use of nebulised treatment when applicable (see 9 for further refs). Aerosols generated by a nebuliser is derived from a medication solution and is not a bioaerosol - potentially infectious - as that generated during cough or sneeze. However, nebulisers could generate fugitive emissions during the drug administration, which are added to patient expiration potentially infectious (9). Moreover, aerosol delivery devices, including nebulisers, could be theoretically considered as fomites, and, therefore, required strict hygiene rules before, during and after use (9). Interestingly, it has been reported that, in healthy volunteers, nebulisation of isotonic saline reduced the number of exhaled bio-aerosol particles expired by 72% for up to 6 hours due to modifications of the surface tension and viscous forces acting on lung-lining fluid (13). Whether nebulisation of isotonic saline aerosols may reduce exhaled particle also in patients affected by viral infection, including SARS-CoV-2, is unknown.

Hence, this project aims at investigating the effects of isotonic saline nebulisation in patients with SARS-CoV-2 infection. We hypothesise that isotonic saline nebulisation may transiently reduce the number of exhaled bio-aerosol droplets with no significant diffusion of virus in the environmental caused by the nebulisation.

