2.0 Aims of the Study

The aims of the present projects are twofold:

- 1) To investigate the mass and size distribution of bio-aerosol particles before and after nebulisation of 0.9% saline in inpatients with COVID-19;
- 2) To assess the risk of SARS-CoV-2 spreading in the hospital patient's room environment after 0.9% saline nebulisation.

3. Methods

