3.1 Study design

Single-center, cross-sectional, explorative study.

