3.3 Inclusion criteria

- a) Patients of both genders, aged >18 years admitted to the Careggi University Hospital due to COVID-19;
- b) Subjects capable of giving informed consent to participate, and available to comply with the requirements and procedures foreseen by the study protocol.

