3.6 Outcome endpoints

Endpoints will be the count of bio-aerosol exhaled particles within a preselected size-selective range (see protocol and study procedures), as well as changes in SARS-CoV-2 degrees in the hospital patient's room environment after 0.9% saline nebulisation.

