3.8 Sample size and data analysis

Due to the explorative nature of the study, a formal assessment of study power will not be performed. However, based on previous studies performed on healthy subjects (13), we estimate that about 10 patients will be sufficient to obtain the data. Parametric variables will be presented as mean \pm SD, with their minimum, maximum and median, while the discrete data will be presented in contingency tables with percentages. Paired t-test will be used to assess differences in the particle size distribution as well as in the SARS-Cov-2 levels before and after nebulisation. The value for the statistical significance will be $P < 0.05$.

4. Safety

All adverse events occurring during thorough the study will be recorded and documented by the Principal Investigator. Any serious adverse event will be reported as soon as possible to the independent Ethics Committee approving the study, according to the current local and national regulations. Expedite reporting will be performed by the Principal Investigator in case of any suspected, unexpected, serious adverse reaction or in case of other safety issues that qualify for expedite reporting, in accordance with the European Directive 2001/20/EC

5. Ethical Considerations

The protocol has been written, and the study will be conducted according to the Declaration of Helsinki and the ICH Harmonized Tripartite Guidelines for Good Clinical Practice. Furthermore, the study will be conducted in accordance with the Ministerial Decree of 17 December 2004.

The final protocol and the final version of the informed consent form will be approved by the local independent ethics committee (IEC) before the study can be commenced. The Principal Investigator is also responsible for informing the IEC of any amendment to the protocol. The Principal Investigator will provide the IEC with reports of Serious Adverse Events from the study site as per local and national requirements. The Principal Investigator will ensure that the patients are given full and adequate oral and written information about the nature, purpose, possible risk and benefit of the study. Patients must also be notified that they are free to discontinue from the study at any time. The patients will be given the opportunity to ask questions and allowed time to consider the information provided. All patients will be requested to provide a signed and dated informed consent before conducting any study-related procedures.

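### The hypothesis of no significant viral spread is paired with a test for differences in about 10 patients, whose non-significance could not support it

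*Protocol*

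**What the plan says.** The closing paragraph of the introductory text states the hypothesis: a transient fall in exhaled droplets, "with no significant diffusion of virus in the environmental caused by the nebulisation". Section 2.0 makes this the second aim: "To assess the risk of SARS-CoV-2 spreading in the hospital patient's room environment after 0.9% saline nebulisation". Section 3.6 names the endpoint as "changes in SARS-CoV-2 degrees in the hospital patient's room environment after 0.9% saline nebulisation", with no threshold for a relevant change.

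Section 3.8 gives the method for both endpoints: "Paired t-test will be used to assess differences in the particle size distribution as well as in the SARS-Cov-2 levels before and after nebulisation". Significance is set at P<0.05. The section says that power will not be formally assessed, and that "based on previous studies performed on healthy subjects (13), we estimate that about 10 patients will be sufficient to obtain the data". The introductory text reports that healthy-subject study only as a 72% fall in exhaled particles; nothing on airborne virus is taken from it. Section 3.1 labels the study "Single-center, cross-sectional, explorative study".

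**The concern.** For virus in the room, the hoped-for answer is no increase. That is the null hypothesis of the only test named. A test for differences can give evidence of an increase. When it fails to reject, it does not show that an increase is absent, least of all in a small sample. The word significant in the hypothesis has no definition in the protocol other than the P<0.05 threshold, and there is no margin or confidence-limit rule to put in its place.

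The sample size does not help, because its stated basis concerns the other endpoint. Sparse data are also foreseeable. The introductory text reports that "one study reports not to find the virus in hospital air samples near COVID-19 patients", and the eligibility criteria require admission due to COVID-19 but no recent positive respiratory test. A t-test behaves badly when most values are non-detects.

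The introductory text says that guidelines conflict on nebuliser use and that robust evidence is lacking. A statement of no significant diffusion would feed into that debate, and any error would fall on staff and other patients.

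**Working it through.** **Plan's own figure.** About 10 patients cannot be reproduced. The protocol gives no SD, effect size, power or margin for either endpoint.

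**Inputs.** From section 3.8: n = 10 and alpha = 0.05. Assumed: a two-sided test (sidedness is not stated), one before and one after value per patient, and every SD and margin below.

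**1. Power of the paired t-test.** Let d be the true mean difference divided by the SD of the paired differences. Power is the probability that a noncentral t with 9 df and noncentrality d × √10 falls beyond the critical value of ±2.262. For d = 0.5 the noncentrality is 0.5 × 3.162 = 1.58.

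| True rise (SD of paired differences) | Power | Missed |
|---|---|---|
| 0.3 | 14% | 86% |
| 0.5 | 29% | 71% |
| 0.8 | 62% | 38% |
| 1.0 | 80% | 20% |
| 1.2 | 92% | 8% |

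The rise detectable with 80% power is 0.996 SD. It would be 1.16 SD with 8 patients and 0.89 SD with 12. The 95% confidence interval has a half-width of 2.262/√10 = 0.72 SD.

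**2. On a log10 viral-load scale (assumed SDs).** A doubling is log10(2) = 0.301, so d = 0.301/SD. The fold rise detectable with 80% power is 10^(0.996 × SD).

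| Assumed SD of log10 differences | Power for a doubling | Rise detectable with 80% power |
|---|---|---|
| 0.3 | 81% | 2.0-fold |
| 0.5 | 40% | 3.2-fold (3.15) |
| 0.7 | 23% | 5.0-fold |
| 1.0 | 14% | 9.9-fold |

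The answer depends heavily on an SD that the protocol does not give.

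**3. A check that needs no SD.** Suppose all 10 rooms are negative before (scored as one fixed value), 3 turn positive after and 7 stay negative. Let the three rises all equal c.

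- Mean difference = 3c/10 = 0.3c.
- Variance = 10 × 0.3 × 0.7 × c²/9 = 0.2333c², so SD = 0.483c.
- Standard error = 0.483c/√10 = 0.1527c.
- t = 0.3/0.1527 = 1.96 on 9 df, P = 0.081.

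c cancels, so the viral load does not matter. Unequal rises with the same sum have a larger sum of squares, hence a larger SD and a smaller t. P is therefore at least 0.081 for any three conversions.

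**4. All samples negative.** Every difference is 0, the SD is 0, and t = 0/0 is undefined. The exact limit is still available. With 0 of 10 conversions, the upper limit for the true proportion is 1 − 0.05^(1/10) = 26% (one-sided 95%) or 1 − 0.025^(1/10) = 31% (two-sided 95%).

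**5. If a margin were used.** With a true difference of 0 and one-sided 0.025, 80% power needs 90, 34, 15 or 10 patients for a margin of 0.3, 0.5, 0.8 or 1.0 SD. With 10 patients, power to exclude a rise of 0.5 SD is 29%.

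**The case against.** The strongest reply is that the protocol never says a non-significant result will be taken as proof of safety. The hypothesis is worded tentatively, the second aim is to assess a risk, the study calls itself explorative, and the lack of a power assessment is openly stated. Intervals and the handling of non-detects may be in an analysis plan that is not shown. All of that stands: a reader might infer that the trial will equate non-significance with safety, but no section says so. What remains is that the stated hypothesis and the stated test do not fit each other, and the protocol offers no other criterion for virus. An explorative label excuses the missing power calculation, not that mismatch.

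A reader might also infer that the trial could not see harm at all, or would usually miss an important rise. Neither is supported. A rise of about 1 SD has 80% power, and with a log10 SD of 0.3 even a doubling has 81%. The protocol defines no important rise. Averaging over three control samplings and using five pumps may reduce the SD.

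Nor is an all-negative result to be expected as a matter of course. Patients must be admitted due to COVID-19, and the introductory text also cites a manikin study that detected virus at two metres. Section 3.8 provides contingency tables for discrete data, so detection could be tabulated. These points make the sparse-data case possible rather than probable. They do not give the t-test a valid use there.

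**Conclusion.** The point holds in this form: the named test cannot support the stated hypothesis on virus, and the stated basis for about 10 patients does not cover that endpoint. The protocol does not support the stronger statements that it declares non-significance to be safety, or that the trial could see no harm.

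Three parts of the size need no assumed SD in viral-load units: a 0.5 SD rise is missed about 71% of the time, three conversions among 10 previously negative rooms cannot reach P<0.05, and all-negative data leave the test undefined. These rest on 10 complete pairs and a two-sided test; the last two also need non-detects scored as one fixed value. Power for a doubling (81% to 14%) rests wholly on the assumed log10 SD of 0.3 to 1.0. Severity: should be fixed.

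**What to change.** Change section 3.8 and the wording of the hypothesis:

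1. Do not use the t-test P-value as the criterion for the second aim. Among patients whose room air was negative before, report how many turn positive after, with an exact (Clopper-Pearson) upper 95% limit. Where virus is quantifiable, also report the after/before change with its confidence interval.
2. State that P≥0.05 will not be read as absence of spread. Claim no relevant increase only if the upper limit lies below a margin that the sponsor states in advance; otherwise conclude that the question is not determined.
3. If no air sample is positive before or after, report that with its exact upper limit and say that the t-test is not computable. Do not restrict the analysis to patients with a positive control filter. Selecting on a high baseline would push the after/before ratio down through regression to the mean, and would remove the patients in whom a conversion can be seen.
4. State that the figure of about 10 refers to the particle endpoint only.

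The cost is rewording and agreeing a margin; no extra patients are needed to report this way. The price is a weaker permitted conclusion. Limits will be wide with 10 patients, so not determined is a likely outcome. Excluding a rise of 0.5 SD with 80% power would take 34.

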2.0 Aims of the Study

The aims of the present projects are twofold:

- 1) To investigate the mass and size distribution of bio-aerosol particles before and after nebulisation of 0.9% saline in inpatients with COVID-19;
- 2) To assess the risk of SARS-CoV-2 spreading in the hospital patient's room environment after 0.9% saline nebulisation.

3. Methods

3.1 Study design

Single-center, cross-sectional, explorative study.

3.2 Study Duration

Estimated recruitment period: 4 months

Total study duration: approximately 6 months

3.3 Inclusion criteria

- a) Patients of both genders, aged >18 years admitted to the Careggi University Hospital due to COVID-19;
- b) Subjects capable of giving informed consent to participate, and available to comply with the requirements and procedures foreseen by the study protocol.

3.4 Exclusion criteria

- a) Patients with COVID-19 requiring non-invasive or invasive mechanical ventilation;
- b) Patients with COVID-19 requiring high ($FiO_2 > 40\%$) level of supplemental oxygen or those requiring oxygen delivery via face mask;

- c) Inability to provide a signed informed consent;
- d) Any disease that, at the judgment of the investigator, may interfere with the study procedures.

3.5 Withdrawal of Subjects

Patients must be withdrawn under the following circumstances:

- a) the patient wishes to be withdrawn (withdrawal of consent)
- b) major protocol violation considered to be relevant by the Investigator

Whenever a patient is prematurely withdrawn from trial participation, the reason will be reported on the clinical report form.

3.6 Outcome endpoints

Endpoints will be the count of bio-aerosol exhaled particles within a preselected size-selective range (see protocol and study procedures), as well as changes in SARS-CoV-2 degrees in the hospital patient's room environment after 0.9% saline nebulisation.

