3.7 Protocol and study procedures

All study procedures will be performed during 2 days at least 24 hours apart. Air sampling of the hospital patient's room environmental will be obtained according to the ISPE guidelines for the monitoring of pharmaceutical powders in working environments (14). In particular, five suction

XR5000 pumps (SKC Inc., Eighty Four, PA) containing a filter and running at 5 L/min for 15-20 minutes will be positioned around the patient's bed at different heights and distances (Figure 1) to allow control (i.e. before saline nebulisation) air samples collection. During the air-sampling period, patients will be free to talk and/or cough. After sampling for 15-20 min, the airborne viral load captured within the pump filter will be detected and quantified using a real-time polymerase chain reaction assay. The control air sampling will be repeated for three times at least 2 hours apart to obtain an average viral load. After sampling of control air, each patient will be requested to breathe normally for 3-5 min through a mouthpiece connected to a sampling T adapter, with one end of the T sampling connected to a six-channel optical particle counter (OPC, Climet, Ultimate 100, Redlansa, CA) to measure expired particle count and size. Each channel on the OPC tabulates particle counts within a size-selective range of six bins (0.3-0.5 μ m, 0.5-1 μ m, 1-3 μ m, 3-5 μ m, 5-10 μ m and >10 μ m). The other end of the T sampling will be connected to a Delbag-Luftfilter air filter (COPULAR CKL Macropur-F Acelan, GEA, Berlin), for removal of any airborne particulates from the inhaled ambient air stream (Figure 2). All the above reported procedures will be repeated on the subsequent day before and 5, 30, 60 and 120 min after nebulisation of 0.9% saline delivered by means of a PARI LC Plus Jet nebuliser (PARI, Starnberg, Germany) connected to a compressed air source at 18 psi.

Cleaning and disinfection of the OPC will be carried out at the end of each investigation with vaporized hydrogen peroxide as suggested by Climet Instruments Company.

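### The particle endpoint's preselected size range is never selected, so up to 24 bin-by-time comparisons could each count as the result at P<0.05

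*Protocol*

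**What the plan says.** Section 3.6 of the protocol defines the particle endpoint as follows: "Endpoints will be the count of bio-aerosol exhaled particles within a preselected size-selective range (see protocol and study procedures", so the reader is sent to section 3.7 for the range.

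Section 3.7 does not choose one. It says: "Each channel on the OPC tabulates particle counts within a size-selective range of six bins", and gives the limits of all six, from 0.3-0.5 µm to above 10 µm. It schedules the measurements "before and 5, 30, 60 and 120 min after nebulisation of 0.9% saline", which is one baseline and four later times, and none of the four is marked as the main one.

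Section 3.8 gives the analysis: "Paired t-test will be used to assess differences in the particle size distribution as well as in the SARS-Cov-2 levels before and after nebulisation". The significance threshold is P<0.05. No main bin, main time, summary measure, order of testing or adjustment is stated.

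Sections 3.1 and 3.8 call the study explorative, and 3.8 gives that as the reason for having no formal power assessment. The background nevertheless ends with a directional hypothesis: that saline nebulisation may transiently lower the number of exhaled droplets.

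**The concern.** The word 'preselected' promises a choice that the protocol does not contain. A statistical analysis plan could add detail, but it would not make the cross-reference in 3.6 correct.

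The analysis sentence does not close the gap. A paired t-test compares one mean difference, so it cannot by itself test a distribution over six bins. Applying it requires either several tests or a summary measure, and the protocol names neither.

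With about 10 patients and a fixed threshold, any bin at any time that reaches P<0.05 could be put forward as the effect, and a reader could not tell it from the best of many chance results. The question behind the hypothesis, whether exhaled particle number falls, would have no single answer.

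**Working it through.** **Inputs from the protocol**
- Size bins: 6 (3.7).
- Times after nebulisation: 4, each compared with the value before it (3.7).
- Test and level: paired t-test, P<0.05 (3.8). Sidedness is not stated; two-sided is assumed.
- Patients: about 10 (3.8).
- Correlation between bins and between times: not given, so a range is assumed.

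The protocol states no overall error rate, so there is no figure of its own to reproduce.

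**Number of comparisons**

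6 bins x 4 times = 24. This is the largest set that the text allows for particles. Virus measurements are not counted.

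**If the tests were independent and there were no effect**
- At least one P<0.05 in either direction: 1 - 0.95^24 = 0.708.
- At least one significant reduction: 1 - 0.975^24 = 0.455, against a nominal 0.025.
- Expected number with P<0.05: 24 x 0.05 = 1.2. This holds whatever the correlation.

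**Why independence is the upper end**

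The six bins come from the same breath sample, and the four times share one baseline. With equal, independent errors of variance s² at each time, every change from baseline has variance 2s², and two changes have covariance s² through the common baseline. Their correlation is therefore s²/2s² = 0.5 from the baseline alone.

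**With correlation**

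20,000 null data sets were simulated per setting, with n = 10, two-sided paired t-tests, and equal correlation among bins and among times. Repeat runs agree to about one percentage point.

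| Bin correlation | Time correlation | Any P<0.05 | Any significant reduction |
|---|---|---|---|
| 0 | 0 | 71% | 46% |
| 0.3 | 0.5 | 61% | 34% |
| 0.5 | 0.5 | 56% | 30% |
| 0.7 | 0.7 | 42% | 21% |
| 0.9 | 0.9 | 22% | 11% |

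The nominal values are 5% and 2.5%. Even the lowest row is more than four times nominal (22/5 = 4.4; 11/2.5 = 4.4).

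**What narrowing would do (independence again)**
- One bin at all four times: 1 - 0.95^4 = 0.185.
- All six bins at one time: 1 - 0.95^6 = 0.265.
- One measure at one time, or one summary over times: 0.05.

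Fixing only the bin or only the time is therefore not enough.

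**The case against.** **The cross-reference can be read as resolving.** Sections 3.6 and 3.7 use the same phrase for a size range, and the counter fixes its bin limits in advance, so all six bins may be what was preselected. That reading is fair, but all six bins are then endpoints and the multiplicity is unchanged.

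**The 24 tests are inferred.** Section 3.8 has one sentence on the t-test and does not say that each bin is tested at each time. Details of multiplicity are often left to a statistical analysis plan, which may exist here. This stands as a limit: 24 is a maximum, not a list in the plan. What remains is that nothing in the protocol narrows it.

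**The study is exploratory.** Family-wise control is not a settled requirement for about 10 exploratory patients. This lowers the weight of the point. It does not remove it, because the protocol keeps a significance threshold and a directional hypothesis.

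**The 71% is too high for this design.** This stands. A reader might infer that a false significant particle effect is more likely than not. That needs weak correlation, which the shared baseline and shared breath sample make unlikely, and it counts false increases too. For a false reduction the chance is below one half even under independence (46%).

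**Wider counts are not supported.** A reader might add virus tests, for example one per pump and time. The protocol proposes no per-pump testing, and virus spread is a separate aim in section 2.0.

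**Conclusion.** The point holds in a limited form. Section 3.6 refers to a selection that 3.7 does not make, and 3.8 attaches a significance threshold without saying which particle comparison it applies to. Up to 24 comparisons qualify.

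Under no effect, the chance of at least one P<0.05 is at most 71% and about 22% to 61% over the positive correlations assumed here. For a false reduction it is about 11% to 46%. These figures assume that all 24 comparisons are made, two-sided, in 10 patients. The correlations are assumptions, not protocol values.

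The documents do not support saying that a false finding is more likely than not, or that the plan prescribes 24 separate tests. Given the exploratory purpose, this is a cheap improvement rather than a flaw that invalidates the study.

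**What to change.** **Section 3.6.** Before data are seen, name one main particle measure and one main time or summary over times. An example is the total count over all six bins on a log scale, as change from the pre-nebulisation value on the second study day. The time or summary should suit a transient effect. A per-litre scale would need a sampled volume, which 3.7 does not state. Correct the reference to 3.7 to match.

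**Section 3.8.** Test that measure once at 0.05; a paired t-test on one value per patient is enough, and a more elaborate model is optional. Report the bin- and time-specific results, which serve the size-distribution aim, as estimates with 95% confidence intervals, either without significance claims or Holm-adjusted.

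Keeping all 24 tests under a Bonferroni limit would cost far more: 0.05/24 = 0.0021 per test. With 10 patients, the mean change detectable with 80% power would rise from about 1.00 to about 1.69 standard deviations of the paired differences.

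**Cost.** Wording in two sections; no new patients, procedures or measurements. There would be fewer individual significant results to report, and a summary over all four times may dilute a short-lived effect, which is why the choice of time needs thought.
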